12.3.4. Justification of Pooling

The poolability of data by center will be tested among the NG4 PMCF Cohort. This analysis will be performed to determine whether there are NG4 PMCF endpoint differences from center-to-center.

Center-to-center heterogeneity will be assessed by performing random effects logistic regression analysis.

Participating center will be added into the model as a random effect. Centers will be deemed to be heterogeneous if the variance of the random center effect is found to significantly differ from zero. A significance level of 15% will be used for each test.

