12.1.2.2. Sample Size

Due to a lack of hypotheses for this objective, the sample size cannot be determined through traditional statistical powering techniques. It is, however, desired to have a high degree of confidence in the CRT Response rates obtained in the study. In order to obtain a two-sided 95% confidence interval width of the overall SMART Registry CRT Response rate that does not exceed 5%, a total of 2000 subject enrollments are required. Additionally, it is expected that with a total of 2000 enrollments, each subgroup analysis will include a sufficient sample of approximately 50 subjects.

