12.1.2.3. Statistical Methods

The Clinical Composite Score allows for three levels of CRT Response: Improved, Unchanged or Worsened. The number and percent of SMART Registry subjects contributing to each level of CRT Response will be calculated.

CRT Response rates will be compared between selected subgroups. Due to the ordinal nature of the three CRT response levels defined by the Clinical Composite Score, statistical tests accounting for ordinality of response will be used, when appropriate. In analyses comparing two subgroups, a Cochran-Armitage test for trend will be employed. If more than two subgroups will be compared, a cumulative logit model or some other appropriate test will be used.

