12.1.3.2. Hypotheses

The following hypotheses will be evaluated to evaluate the safety of the NG4 device:

$$H_0: \text{PG-related CFR at 36 months} \leq 88.5\%$$

$$H_A: \text{PG-related CFR at 36 months} > 88.5\%$$

To ensure that the safety of the NG4 devices with LV MSP enabled is acceptable, the performance goal for this endpoint was based on the observed safety of prior approved Boston Scientific devices in the following studies: CAPTIVATE, LSS of 4-SITE, MADIT CRT, MultiSENSE, NAVIGATE X4. Prior devices in these studies have shown a PG-related complication-free rate of 98.5% through 36 months of follow-up. The performance goal of 88.5% was derived from the prior performance of 98.5% minus 10% to account for variability in the estimate. Expected performance of the NG4 device was based on the observed rate of prior devices.

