12.1.3.4. Statistical Methods

The Primary Endpoint will be calculated using Kaplan-Meier methodology. The 95% one-sided pointwise log-log confidence limit of the PG-related complication-free rate at 36 months will be compared to the performance goal of 88.5%. If the lower confidence limit exceeds 88.5%, the null hypothesis will be rejected.

12.2. *General Statistical Methods*

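### Center heterogeneity is tested only on the PMCF safety endpoint, where about one event is expected, while the registry comparison of site-driven optimization methods has no center term

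*Combined protocol and SAP*

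**What the plan says.** Section 12.3.4 limits the center assessment to one cohort and one endpoint: "The poolability of data by center will be tested among the NG4 PMCF Cohort". The method is given as "Center-to-center heterogeneity will be assessed by performing random effects logistic regression analysis", with the decision rule "Centers will be deemed to be heterogeneous if the variance of the random center effect is found to significantly differ from zero" and the level "A significance level of 15% will be used for each test". The section names no action if centers are found heterogeneous. The endpoint itself is analyzed differently. Section 12.1.3.4 says "The Primary Endpoint will be calculated using Kaplan-Meier methodology".

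For the registry response rate, Section 12.1.2.2 sets a precision target: "In order to obtain a two-sided 95% confidence interval width of the overall SMART Registry CRT Response rate that does not exceed 5" percent, for which it says 2,000 enrollments are needed. Section 12.1.2.3 adds "In analyses comparing two subgroups, a Cochran-Armitage test for trend will be employed", with a cumulative logit model or another suitable test for more than two groups. Section 12.3.3 applies the same trend test to the listed baseline covariates. None of these sections has a center term, a design effect or a clustered variance. Section 6 makes the comparison of response between optimization methods part of the primary objective, and Section 11.4.11 leaves the choice of method to each site's standard of care.

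**The concern.** The plan tests for center differences where there is almost nothing to see, and makes no test or adjustment where there is. With about one complication expected in the whole PMCF cohort, the variance between centers cannot be estimated, so the rule will nearly always find no heterogeneity, whatever the truth. The logistic model also has no place for follow-up time, although about 39% of the cohort is expected to be lost by 36 months. Section 12.3.4 does not say whether those subjects are dropped or counted as event-free.

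The registry may have up to 200 sites, site-assessed NYHA class and no blinding (Section 8.2.1). Responses within a site are therefore likely to be correlated. If the factor being compared also follows the site, as optimization method does, an analysis that treats subjects as independent gives standard errors that are too small and finds differences too often. At stake are the error rate of the comparison named in the primary objective and the width of the overall response interval.

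**Working it through.** **Inputs from the plan.** Complication-free rate: "Prior devices in these studies have shown a PG-related complication-free rate of 98.5% through 36 months of follow-up" (Section 12.1.3.2), also taken as the expected NG4 rate. PMCF size 103, target 63 at 36 months, attrition 15% a year (12.1.3.3). Registry 2,000 subjects (12.1.2.2), up to 200 sites (8.1). Response about two-thirds in NYHA III-IV and about 10 points lower in I-II (Section 4).

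**Assumed, not in the documents.** ICC 0.01-0.10; 10 or 20 subjects per site; 10, 20 or 40 PMCF centers; 15% incomplete scores in the registry, borrowed from the PMCF attrition figure.

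**1. The plan's PMCF size reproduces.** 63 / 0.85³ = 63 / 0.614 = 102.6, so 103. The share lost by 36 months is 1 − 0.614 = 38.6%.

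**2. Expected PMCF events.** Constant hazards: λ = −ln(0.985)/3 = 0.00504 for complications and μ = −ln(0.85) = 0.1625 for attrition, per year. Events = 103 × λ/(λ+μ) × (1 − e^(−3(λ+μ))) = 103 × 0.0301 × 0.395 = 1.22. The bounds are 63 × 0.015 = 0.95 and 103 × 0.015 = 1.55 (no attrition). With a Poisson mean of 1.22, P(0 events) = 29% and P(0 or 1) = 65%. With no event there is nothing to fit, and a single event cannot show clustering.

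**3. Behavior of the poolability test.** Likelihood-ratio test of zero center variance in a random-intercept logistic model, 103 subjects in 10, 20 or 40 centers, nominal level 15%, 4,000 runs per setting. Full follow-up was assumed, which favors the test. The ranges cover the center counts and two reference distributions (the boundary mixture and the plain chi-square).

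| Center SD (logit scale) | Rejection rate |
|---|---|
| 0 | 1-3% |
| 1.0 | 3-7% |
| 1.5 | 8-13% |

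A separate simulation at an event probability of 1.3% (20 or 40 centers, 400 runs) gave 1.5-3% with no heterogeneity, 6-8% at SD 1 and 16-19% at SD 2. An SD of 1 means that centers one SD above and below the mean differ by an odds ratio of e² = 7.4. Even then the test rejects less often than its nominal level.

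**4. Registry trend test.** Three ordered response levels (about 66% improved, 80% improved or unchanged), a latent-normal site effect, nominal 5%, 1,500 runs. The ICC here is on the latent scale.

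| Grouping factor | ICC | 200 sites × 10 | 100 sites × 20 |
|---|---|---|---|
| Unrelated to site | 0.02-0.10 | 4.3-4.9% | 4.7-5.3% |
| Partly follows site | 0.02-0.10 | 5.0-8.8% | 6.1-10.0% |
| Chosen by site | 0.02 | 5.9% | 7.5% |
| Chosen by site | 0.05 | 8.5% | 12.3% |
| Chosen by site | 0.10 | 12.3% | 17.9% |

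**5. Registry interval.** Width = 2 × 1.96 × √(p(1−p) × DEFF / n), with DEFF = 1 + (m − 1) × ICC. Under independence the 5% target needs 1,537 subjects at p = 0.5 or 1,366 at p = 2/3, so the plan's 2,000 is more than simple random sampling requires. At n = 2,000 the independent width is 4.4% or 4.1%. With clustering:

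| ICC | m = 10: p = 0.5 / 2/3 | m = 20: p = 0.5 / 2/3 |
|---|---|---|
| 0.01 | 4.6% / 4.3% | 4.8% / 4.5% |
| 0.02 | 4.8% / 4.5% | 5.2% / 4.9% |
| 0.05 | 5.3% / 5.0% | 6.1% / 5.8% |
| 0.10 | 6.0% / 5.7% | 7.5% / 7.0% |

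The m = 20 column also stands for 200 unequal sites whose sizes have a coefficient of variation of about 1. The 5% limit holds up to DEFF = (5/4.38)² = 1.30 (p = 0.5) or (5/4.13)² = 1.46 (p = 2/3). In ICC terms that is 0.034 or 0.052 at m = 10, and 0.016 or 0.024 at m = 20. With 1,700 evaluable the independent width is 4.75% (p = 0.5) or 4.47% (p = 0.67), and the tolerated DEFF falls to 1.11 or 1.25.

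**The case against.** The registry has no formal hypotheses and is described as exploratory. Section 12.2.2 claims no alpha control and says results will be read for plausibility and consistency. A site enrollment cap is also in place to limit single-center bias. These points lower the stakes but do not remove the problem. Exploratory intervals and p-values are still read at face value, and a cap limits one site's influence without correcting the variance. The cap itself needs reconciling: Section 12.2.3 gives 200 subjects (10%), while Section 10.4 gives 20% unless the sponsor approves more.

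Three stronger readings are tempting, and the documents do not support them.

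- A reader might infer that the 5% width holds only under independence. It does not: 2,000 subjects leave room for a design effect of 1.30 to 1.46. Whether the limit is broken depends on an ICC, a spread of site sizes and a registry loss rate that the plan does not give.
- A reader might infer that all the trend tests reject too often. Inflation needs a factor that follows the site. Sex, age, diabetes and similar patient-level covariates in Section 12.3.3 stay near 5%.
- A reader might infer that the weak poolability test undermines the PMCF decision. Section 12.1.3.4 rests that decision on the Kaplan-Meier lower limit alone, and Section 12.3.4 attaches no consequence to the pooling result.

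Leave-one-center-out Kaplan-Meier limits might seem a natural replacement. With no events, the log-log limit is undefined. With one event, it becomes undefined once that center is left out. The approach therefore cannot be fully carried out in about 65% of cases.

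**Conclusion.** The point holds in two parts.

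First, the PMCF poolability test is uninformative on the plan's own figures: about 1.2 expected events (0.95-1.55), and rejection in 1-3% of runs without heterogeneity and 3-8% with a center SD of 1. This rests on the planned 98.5% rate and on assumed center counts. The conclusion is the same for 10, 20 and 40 centers.

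Second, the registry analyses make no allowance for center, and this matters for comparisons that follow site practice, above all optimization method. The type I error there is about 6-18% instead of 5%, for an assumed ICC of 0.02-0.10 and 10-20 subjects per site. The overall interval is too narrow for any positive ICC, but whether it passes 5% cannot be settled from the documents.

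This is a worthwhile and inexpensive correction to the analysis plan. It does not threaten the PMCF endpoint decision.

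**What to change.** - In Section 12.3.4, replace the random-effects logistic test with a descriptive listing of PMCF events by center, and do not offer it as evidence that centers can be pooled.
- Assess center heterogeneity on the 12-month Clinical Composite Score, with a cumulative logit model that includes a random site effect, and report the ICC.
- Use site-clustered variance, or the random-site model, for the overall response interval and for comparisons of optimization methods and other site-driven factors. The planned Cochran-Armitage test can stay for patient-level covariates.
- In Section 12.1.2.2, state that at 2,000 subjects the 5% width holds up to a design effect of about 1.30 (p = 0.5) or 1.46 (p = 2/3), and at 1,700 evaluable (assumed 15% loss) up to about 1.11 (p = 0.5) or 1.25 (p = 0.67).
- Reconcile the site cap between Sections 10.4 and 12.2.3.

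No new data are needed, and Section 12.3.5 allows such changes if they are documented before the analyses. The cost is SAP wording, a little more analysis work in standard software, and a slightly wider registry interval. The change corrects the error rate. It does not remove confounding of optimization method with other site differences.

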12.3.5. Changes to Planned Analyses

Any changes to the planned statistical analyses made prior to performing the analyses will be documented in a Statistical Analysis Plan approved prior to performing the analyses.

Changes from the planned statistical methods after performing the analyses will be documented in the clinical study report along with a reason for the deviation.

13. Data Management

13.1. *Data Collection, Processing, and Review*

Subject data will be recorded in a limited access secure electronic data capture (EDC) system.

The clinical database will reside on a production server hosted by EDC System. All changes made to the clinical data will be captured in an electronic audit trail and available for review by the sponsor or its representative. The associated RAVE software and database have been designed to meet regulatory compliance for deployment as part of a validated system compliant with laws and regulations applicable to the conduct of clinical studies pertaining to the use of electronic records and signatures. Database backups are performed regularly.

The Investigator provides his/her electronic signature on the appropriate electronic case report forms (eCRFs) in compliance with local regulations. A written signature on printouts of the eCRFs must also be provided if required by local regulation. Changes to data previously submitted to the sponsor require a new electronic signature by the Investigator acknowledging and approving the changes.

Visual and/or electronic data review will be performed to identify possible data discrepancies. Manual and/or automatic queries will be created in the EDC system and will be issued to the site for appropriate response. Site staff will be responsible for resolving all queries in the database.

13.2. *Data Retention*

The Principal Investigator or his/her designee or participating site will maintain, at the investigative site, all essential study documents and source documentation that support the data collected on the study subjects in compliance with ICH/GCP guidelines. Documents must be retained for at least 2 years after the last approval of a marketing application or until at least 2 years have elapsed since the formal discontinuation of the registry. These documents will be retained for a longer period of time by agreement with BSC or in compliance with other country/regional/local regulations.

The Principal Investigator or his/her designee will take measures to ensure that these essential documents are not accidentally damaged or destroyed. If for any reason the Principal Investigator or his/her designee withdraws responsibility for maintaining these essential documents, custody must be transferred to an individual who will assume responsibility and BSC must receive written notification of this custodial change. Sites are required to inform Boston Scientific in writing where paper or electronic files are maintained in case files are stored off site and are not readily available.

14. Amendments

If a protocol revision is necessary which affects the rights, safety or welfare of the subject or scientific integrity of the data, an amendment is required. Appropriate approvals (e.g., IRB/EC/FDA/CA) of the revised protocol must be obtained prior to implementation.

15. Deviations

An Investigator must not make any changes or deviate from this protocol, except to protect the life and physical well-being of a subject in an emergency. An investigator shall notify the sponsor and the reviewing IRB/EC of any deviation from the protocol to protect the life or physical well-being of a subject in an emergency, and those deviations which affect the scientific integrity of the clinical investigation. Such notice shall be given as soon as possible, but no later than 5 working days after the emergency occurred, or per prevailing local requirements, if sooner than 5 working days.

All deviations from the protocol, with the reason for the deviation and the date of occurrence, must be documented and reported to the sponsor using EDC. Sites may also be required to report deviations to the IRB/EC, per local guidelines and government regulations.

Deviations will be reviewed and evaluated on an ongoing basis and, as necessary, appropriate corrective and preventive actions (including IRB/EC notification, site re-training, or site discontinuation/termination) will be put into place by the sponsor.

16. Compliance

16.1. *Statement of Compliance*

This study will be conducted in accordance post market clinical follow up guidelines and will follow the applicable sections of ISO 14155(Clinical Investigation of Medical Devices for Human Subjects – Good Clinical Practice), the relevant parts of the ICH Guidelines for Good Clinical Practices, ethical principles that have their origins in the Declaration of Helsinki, and pertinent individual country laws and regulations. The study shall not begin until the required approval/favorable opinion from the IRB/EC and/or regulatory authority has been obtained, if appropriate. Any additional requirements imposed by the IRB/EC or regulatory authority shall be followed, if appropriate.

16.2. *Investigator Responsibilities*

The Principal Investigator of an participating site is responsible for ensuring that the study is conducted in accordance with the Clinical Study Agreement, the clinical investigation plan/, ISO 14155, ethical principles that have their origins in the Declaration of Helsinki, any conditions of approval imposed by the reviewing IRB/EC, and prevailing local and/or country laws and/or regulations, whichever affords the greater protection to the subject.

The Principal Investigator's responsibilities include, but are not limited to, the following.

- Prior to beginning the study, sign the Clinical Study Agreement and comply with the Investigator responsibilities as described in such Agreement.
- Prior to beginning the study, sign the Protocol Signature page documenting his/her agreement to conduct the study in accordance with the protocol.

- Provide his/her qualifications and experience to assume responsibility for the proper conduct of the study and that of key members of the site team through up-to-date curriculum vitae or other relevant documentation and disclose potential conflicts of interest, including financial, that may interfere with the conduct of the clinical study or interpretation of results.
- Make no changes in or deviate from this protocol, except to protect the life and physical well-being of a subject in an emergency; document and explain any deviation from the approved protocol that occurred during the course of the clinical investigation.
- Create and maintain source documents throughout the clinical study and ensure their availability with direct access during monitoring visits or audits; ensure that all clinical-investigation-related records are retained per requirements.
- Ensure the accuracy, completeness, legibility, and timeliness of the data reported to the sponsor in the CRFs and in all required reports.
- Record, report, and assess (seriousness and relationship to the device/procedure) every adverse event as applicable per the protocol and observed device deficiency.
- Report to sponsor, per the protocol requirements, all SAEs and device deficiencies that could have led to a SADE and potential/USADE or UADE.
- Report to the IRB/EC and regulatory authorities any SAEs and device deficiencies that could have led to a SADE and potential/USADE or UADE, if required by the national regulations or this protocol or by the IRB/EC, and supply BSC with any additional requested information related to the safety reporting of a particular event.
- Allow the sponsor to perform monitoring and auditing activities, and be accessible to the clinical research monitor or auditor and respond to questions during monitoring visits or audit(s).
- Allow and support regulatory authorities and the IRB/EC when performing auditing activities.
- Ensure that informed consent is obtained in accordance with applicable laws, this protocol and local IRB/EC requirements.
- Provide adequate medical care to a subject during and after a subject's participation in a clinical study in the case of adverse events, as described in the Informed Consent Form (ICF).
- Inform the subject of the nature and possible cause of any adverse events experienced.
- As applicable, provide the subject with necessary instructions on proper use, handling, storage, and return of the device when it is used/operated by the subject.
- Inform the subject of any new significant findings occurring during the clinical investigation, including the need for additional medical care that may be required.
- Provide the subject with well-defined procedures for possible emergency situations related to the clinical study, and make the necessary arrangements for emergency

treatment, including decoding procedures for blinded/masked clinical investigations, as needed.

- Ensure that clinical medical records are clearly marked to indicate that the subject is enrolled in this clinical study.
- Ensure that, if appropriate, subjects enrolled in the registry are provided with some means of showing their participation in the clinical investigation, together with identification and compliance information for concomitant treatment measures (contact address and telephone numbers shall be provided).
- Inform, with the subject's approval or when required by national regulations, the subject's personal physician about the subject's participation in the clinical investigation.
- Make all reasonable efforts to ascertain the reason(s) for a subject's premature withdrawal from registry while fully respecting the subject's rights.
- Ensure that an adequate investigation site team and facilities exist and are maintained and documented during the registry.
- Ensure that maintenance and calibration of the equipment relevant for the assessment of the registry is appropriately performed and documented, where applicable.

16.2.1. Delegation of Responsibility

When specific tasks are delegated by an investigator, including but not limited to conducting the informed consent process, the Principal Investigator is responsible for providing appropriate training and adequate supervision of those to whom tasks are delegated. The investigator is accountable for regulatory violations resulting from failure to adequately supervise the conduct of the clinical study.

16.3. Institutional Review Board/ Ethics Committee

Prior to gaining Approval-to-Enroll status, the participating site will provide to the sponsor documentation verifying that their IRB/EC is registered or that registration has been submitted to the appropriate agency, as applicable according to national/regulatory requirements.

A copy of the written IRB/EC and/or competent authority approval of the protocol (or permission to conduct the study) and Informed Consent Form, must be received by the sponsor before recruitment of subjects into the study. Prior approval must also be obtained for other materials related to subject recruitment or which will be provided to the subject.

Annual IRB/EC approval and renewals will be obtained throughout the duration of the study as required by local/country or IRB/EC requirements. Copies of the Investigator's reports and the IRB/EC continuance of approval must be provided to the sponsor.

